4.3 Primary Safety Endpoint Calculation

The primary safety endpoint will test the proportion of subjects meeting the primary safety endpoint through 3 months post treatment. The hypothesis of interest for the primary safety endpoint is:

$$H_0: P_C - P_T \leq -\delta$$

$$H_a: P_C - P_T > -\delta$$

where P_T and P_C represent proportions of treatment and control subjects, respectively, who meet the primary safety endpoint. Analysis of the primary safety hypothesis will be conducted using a z-test of proportions with a pooled variance and continuity correction, using a non-inferiority margin of 10% and a one-sided significance level of 0.025. If non-inferiority is established, a test for superiority at a significance level of 0.025 will be conducted. If it can be established that the rate difference is statistically greater than 0, superiority will also be claimed.

4.4 Sample Size Considerations and Statistical Analyses

The WATER Study is designed as a prospective, randomized, blinded, controlled trial to demonstrate non-inferiority of the AQUABEAM System to TURP with respect to symptom improvement at 6 months. The WATER Study is designed in accordance with FDA's "Guidance for Non-Clinical and Clinical Investigation of Devices Used for the Treatment of Prostatic Hyperplasia (BPH)," published August 17, 2010.

Subjects will be randomly assigned in a 2:1 ratio to treatment with Aquablation or to treatment with TURP. The Primary Effectiveness Endpoint for this clinical trial is change in IPSS from baseline to 6-month evaluation.

Minimum enrollment (N_{\min}) in the WATER trial is 177 subjects (118 Aquablation and 59 TURP) to power at 80% for possible demonstration of superiority for the safety endpoint under an assumption of an endpoint rate of 65% in TURP and 40% in Aquablation, while including a 12% lost to follow-up rate (i.e., 156 evaluable subjects). The primary safety endpoint with 156 subjects evaluable displays over 99% power at a one-sided alpha level of 0.025 to demonstrate non-inferiority within a margin of 10% under an assumption of a true rate of events in the Aquablation group of 40% and expected rate of 65% in the TURP group.

Under an assumption of an effectiveness NIM of 4.7 points and a treatment effect of -1.5 points (i.e., mean change score in Aquablation is 1.5 points lower than TURP) with a standard deviation of 6 points, the sample size of 156 evaluable subjects provides more than 80% power in a test of non-inferiority for the primary effectiveness endpoint.

The trial will utilize a group sequential design with a single interim look and will incorporate a sample size re-estimation (SSR) at the time of the interim look based on promise for superiority on effectiveness. Methods for the SSR have been described in detail [30] [31].

An O'Brien-Fleming (OBF) alpha-spending function will be employed to control for type I error rate on the primary effectiveness endpoint. The maximum enrollment being considered is 270 total enrolled ($N_{\max} = 1.5$ times N_{\min}).

An interim analysis incorporating a SSR will take place when all 177 subjects have been enrolled and completed the 3 month evaluation. The analysis will be performed by an independent statistician with a Data Monitoring Committee (DMC) review. Under the enrollment projection, it is assumed that 67% of the subjects will have completed the 6 month assessment at the time of the interim analysis. At this point, the non-inferiority test for primary effectiveness under an OBF alpha-spending function will be computed. Based on this result, the conditional power to claim superiority (CP_{sup}) on the primary effectiveness endpoint will also be computed. The conditional power (CP_{sup}) will be calculated based on the interim results of the primary effectiveness endpoint, with the specific interest of demonstrating superiority. CP_{sup} is defined as the approach that quantifies the statistical power to yield an answer different from that seen at the interim analysis. The data will be partitioned into three zones based on CP_{sup} unfavorable zone ($CP_{\text{sup}} < 40\%$), promising zone ($40\% \leq CP_{\text{sup}} < 80\%$), and favorable zone ($CP_{\text{sup}} \geq 80\%$). The following decision rules outline the possible outcomes of the interim analysis:

- (i) If the test for non-inferiority for primary effectiveness under an OBF alpha-spending function fails to reject the null hypothesis, there is no increase in sample size and the submission for the primary analysis will take place when all subjects have completed 6 months follow-up.
- (ii) If the test for non-inferiority for primary effectiveness under an OBF alpha-spending function rejects the null hypothesis, and if $CP_{\text{sup}} < 0.4$ or ≥ 0.8 , then there is no increase in the sample size and the study will be submitted to FDA based on the outcome from the interim analysis.

- (iii) If the test for non-inferiority for primary effectiveness under an OBF alpha-spending function rejects the null hypothesis, and if $0.4 \leq CP_{sup} < 0.8$, then the sample size will be increased by just the right amount such that CP_{sup} is increased to 0.8, under a cap of 270 subjects. The range $0.4 \leq CP_{sup} < 0.8$ is called the promising zone for superiority. Specifically, if CP_{sup} is in its promising zone, this decision rule increases the sample size by the smaller of 270 patients or the number needed to boost CP_{sup} to 0.8.

The testing of the safety endpoint for non-inferiority occurs a single time at the time of submission. All safety data will be complete regardless of the outcome of the sample size adaptation and therefore does not require a type-I error adjustment. If the hypothesis for non-inferiority of the safety endpoint is rejected, a test for superiority of the safety endpoint will take place. A decision tree based on the testing of the effectiveness endpoint is outlined below in Figure 10.

[figure not shown]

Figure 10: Decision tree for group sequential interim analysis with SSR

A final IDE clinical study report will be produced and submitted when all subjects have completed the 36-month follow-up visit.

Full details of statistical analyses will be outlined in the Statistical Analysis Plan (SAP).

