## 5.5 Sample Size Calculation

Sample size was reported in the original study protocol. Version G proposed an NIM of 4.7 points (based on an estimated baseline score distribution). With a sample size of 177 randomized subjects (118 A and 59 T), an effect size of -1.5 points, a standard deviation of 6 and a NIM of 4.7 points, the study has adequate power for the primary effectiveness endpoint. Power for the safety endpoint was also high assuming endpoint rates of 65% in T and 40% in A, including a 12% loss to follow-up rate.

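### Stated power of over 99% for safety non-inferiority at 156 evaluable subjects is slightly too high: the protocol's own test gives about 97.9%, and the uncorrected or score test about 98.8%

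*Protocol*

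**What the plan says.** Protocol section 4.4 sets minimum enrolment from the safety superiority test at 80% power; the minimum "is 177 subjects (118 Aquablation and 59 TURP"), which becomes 156 evaluable after 12% loss to follow-up. It then adds a separate power statement for safety non-inferiority: "The primary safety endpoint with 156 subjects evaluable displays over 99% power at a one-sided alpha level of 0.025". The conditions attached are a 10% margin and "a true rate of events in the Aquablation group of 40% and expected rate of 65% in the TURP group".

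Protocol section 4.3 fixes the analysis as a "z-test of proportions with a pooled variance and continuity correction", "using a non-inferiority margin of 10% and a one-sided significance level of 0.025".

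SAP section 5.1 handles the same endpoint differently. It uses a two-sided 95% confidence interval against the 10% margin and takes the p-value from the gsDesign function testBinomial. It mentions neither a pooled variance nor a continuity correction. SAP section 5.5 gives no percentage for safety power and says only that it was high.

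**The concern.** All the inputs to the power figure are in the protocol, so it can be checked against the test the protocol says it will run. That test falls short of 99% at the stated number of subjects.

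Safety non-inferiority is one of two primary endpoints that must both be met for the study to succeed (protocol sections 1.2 and 4.1), and section 4.4 holds the only quantified statement of its power. Power above 99% implies a chance of missing the endpoint below 1% under the design assumptions. With the section 4.3 test that chance is roughly double. What is at stake is the accuracy and reproducibility of a design statement. The size of the trial is not in question.

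**Working it through.** **Inputs**
- Event rates: p_A = 0.40, p_T = 0.65 (protocol 4.4).
- Margin: 0.10. One-sided alpha: 0.025, so z = 1.96 (protocol 4.3 and 4.4).
- Evaluable subjects: 177 × 0.88 = 155.8, taken as 156 (protocol 4.4).
- Split at 2:1: n_A = 104, n_T = 52. The protocol does not print this split; it follows from the allocation ratio.

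**Quantities used below**
- Distance from the assumed truth to the margin: (0.65 − 0.40) + 0.10 = 0.35.
- Unpooled SE: SE1 = √(0.40×0.60/104 + 0.65×0.35/52) = 0.0817.
- Pooled rate: (104×0.40 + 52×0.65)/156 = 0.4833. Pooled SE: SE0 = √(0.4833×0.5167×(1/104 + 1/52)) = 0.0849.
- Continuity correction: c = ½(1/104 + 1/52) = 0.0144.
- SE at the null-hypothesis rates 0.75 and 0.65: SEN = √(0.75×0.25/104 + 0.65×0.35/52) = 0.0786.

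**Step 1. Can the stated figure be reproduced by a normal approximation?**

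| Formula | Argument of Φ | Power |
|---|---|---|
| Null variance at the null rates: Φ((0.35 − 1.96·SEN)/SE1) | 2.397 | 99.17% |
| Unpooled: Φ(0.35/SE1 − 1.96) | 2.322 | 98.99% |
| Pooled under the null: Φ((0.35 − 1.96·SE0)/SE1) | 2.247 | 98.8% |
| Pooled with correction: Φ((0.35 − c − 1.96·SE0)/SE1) | 2.070 | 98.1% |

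The first formula exceeds 99% and the second misses by 0.01 point. The last, which matches section 4.3, misses by about 0.9 point.

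**Step 2. Exact power of the tests themselves**

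For every pair of event counts (x, y) from Bin(104, 0.40) and Bin(52, 0.65), compute the test statistic and add up the joint probabilities where it exceeds 1.96.

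| Test at 104 against 52 | Exact power | Type II error |
|---|---|---|
| Pooled z with continuity correction (protocol 4.3) | 97.9% | 2.1% |
| Pooled z, no correction | 98.8% | 1.2% |
| Unpooled z, no correction | 98.8% | 1.2% |
| Score test (as SAP 5.1 is read here) | 98.8% | 1.2% |

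Shortfall from 99%: 99.0 − 98.8 = 0.2 point, up to 99.0 − 97.9 = 1.1 points.

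**Step 3. Does the sample size depend on this figure?**

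No. Section 4.4 sets the number by safety superiority at 80% power. With the corrected test at 104 against 52, the normal approximation is Φ((0.25 − 0.0144 − 1.96×0.0849)/0.0817) = Φ(0.847) = 80.1%, and exact enumeration gives 81.1%. The calculation that drives enrolment therefore holds.

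**The case against.** The strongest defence is that the protocol does not say how it obtained the figure, and that the figure lies at the upper end of ordinary approximations. One normal approximation gives 99.2% at 104 against 52. The unpooled one gives 98.99%, and 99.04% if the 156 are split 103 against 53. This stands. A reader might infer that no standard calculation can exceed 99% at 156, but that is not so, and the statement cannot be shown to be an arithmetic slip. It does not, however, rescue the statement as a description of the planned test: the exact powers in the working are below 99% for the tests of both documents.

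A second inference to avoid is that the figure was computed on all 177 enrolled subjects. The corrected normal approximation does give 99.1% at 118 against 59. But exact enumeration of the same test there gives 98.9%, and the companion 80% superiority figure reproduces at 156. The documents do not say which number was used.

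It is also fair to say that the 97.9% belongs to a test the SAP does not carry forward, although the protocol defers full analysis detail to the SAP. On the SAP's basis the gap is only about 0.2 point, so a doubling of the type II error applies to the section 4.3 test alone.

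Finally, SAP section 5.5 is not a second instance of the problem. Its statement, "Power for the safety endpoint was also high assuming endpoint rates of 65% in T and 40% in A", is true at 98%. Revision H follows subjects already treated and marks the endpoint as already reported, so the correction changes nothing operational.

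**Conclusion.** The point holds as a minor correction. With 156 evaluable subjects, safety non-inferiority has about 97.9% power under the protocol's own test and about 98.8% under the uncorrected or score test.

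This rests on the protocol's assumed rates of 40% and 65%, on an evaluable split of exactly 104 against 52, and on reading testBinomial as a score test without continuity correction, since the SAP states no options for it. If the SAP's test were continuity-corrected, its power would be expected to lie nearer the 97.9% end.

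Power of 98% to 99% is ample. No sample size, margin or decision rule changes.

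**What to change.** In protocol section 4.4, replace the non-inferiority power statement with wording such as: with 156 evaluable subjects (104 Aquablation, 52 TURP), power for safety non-inferiority is about 98% with the continuity-corrected z-test of section 4.3, and about 98.8% with the uncorrected or score test in the SAP, by exact binomial enumeration. Name the method, so that the figure can be reproduced, and say which of the two tests is primary, since sections 4.3 and SAP 5.1 differ.

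The cost is one or two sentences and a slightly less favourable number. Enrolment stays as it is, and SAP section 5.5 needs no correction on this account.

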4.5 Study Populations for Analysis

4.5.1 Modified Intent-to-Treat (mITT)

The mITT analysis population includes all randomized subjects in whom an intended intervention is initiated. If a patient is found at the time of the procedure to have a condition that results in study exclusion, this patient does not contribute to the mITT cohort. Subjects will be analyzed according to their randomized group assignment. The mITT population is the primary analysis population for both the primary and secondary endpoints.

4.5.2 Per-protocol (PP)

The per-protocol (PP) population will consist of all mITT subjects that:

1. meet critical study eligibility criteria;
2. have no significant protocol deviations; and
3. have evaluable assessment for the primary study endpoints. The PP population will be used for subset analysis of the primary endpoints.

A significant protocol deviation means non-adherence on the part of the subject or investigator to clinically significant protocol-specific inclusion/exclusion criteria, primary objective variable criteria, and/or GCP guidelines.

4.5.3 Safety

The safety analysis population includes all randomized subjects. Secondary safety endpoints including the summary of adverse events in the trial will be analyzed using this analysis population, divided into groups according to actual treatment received.

4.6 Additional Endpoints

The following secondary objectives are intended to support product labeling. The endpoints will be tested in sequential fashion using the Holms step-down procedure for type-I error rate correction if and only if the primary objective passes according to the non-inferiority criteria outlined above. At the conclusion of the trial, the secondary endpoints intended for product labeling will be ordered sequentially from most significant to least significant. The endpoints will then be tested in order at adjusted levels of significance (i.e. E1: 0.05/k, E2: 0.05/k-1; E3: 0.05/k-2; E4: 0.05/k-3; E5: 0.05/k-4;, where k=number of specified endpoints). Once an endpoint fails, all following endpoints will not be tested. Following is a list of secondary endpoints intended to support product labeling:

- Evaluation of the proportion of subjects requiring re-operation and re-intervention through 6 months. The following hypothesis will be tested:

$$H: P_C - P_T > -\delta$$

where P_T and P_C represent proportions of subjects requiring re-operation or re-intervention through 6 months post treatment. The Aquablation group will be declared to be non-inferior to TURP if it can be established that the difference is within the non-inferiority margin of $\delta = 0.10$. The statistical test will be a z-test using pooled variance estimate and no continuity correction. In the case of small counts, an exact procedure will be used. Descriptive statistics and 95% confidence intervals will be calculated.

- Evaluation of the proportion of sexually active subjects reporting a worsening of sexual function through 6 months defined as a decrease of 6 points or more on the IIEF-5 (part of the IIEF-15) or a decrease of 2 points or more on the MSHQ-EjD questionnaires. The following hypothesis will be tested:

$$H_0: P_T = P_C$$

$$H_a: P_T < P_C$$

where P_T and P_C represent proportions of subjects with worsening score on the IIEF-5 and/or the MSHQ-EjD from baseline through 6 months post treatment. The statistical test for superiority will be a z-test using pooled variance estimate and no continuity correction. In the case of small counts, an exact procedure will be used. Descriptive statistics and 95% confidence intervals will be calculated.

- Evaluation of the mean length of hospital stay in the treatment groups. The following hypothesis will be tested:

$$H: \mu_T - \mu_C > 0$$

where μ_T and μ_C is the average length of stay in days in the treatment and control groups, respectively. Statistical summaries will include means, medians, and standard deviation, as well as 95% confidence intervals. A t-test for superiority will be performed to test the hypothesis that μ_T is significantly less than μ_C .

- Evaluation of the mean length of operative time in the treatment groups. The following hypothesis will be tested:

$$H: \mu_T - \mu_C > 0$$

where μ_T and μ_C is the average operative time in minutes in the treatment and control groups, respectively. Statistical summaries will include means, medians, and standard deviation, as well as 95% confidence intervals. A t-test for superiority will be performed to test the hypothesis that μ_T is significantly less than μ_C .

- Evaluation of the mean length of resection time in the treatment groups. The following hypothesis will be tested:

$$H: \mu_T - \mu_C > 0$$

where μ_T and μ_C is the average operative time in minutes in the treatment and control groups, respectively. Statistical summaries will include means, medians, and standard deviation, as well as 95% confidence intervals. A t-test for superiority will be performed to test the hypothesis that μ_T is significantly less than μ_C .

4.7 Handling of Missing Data

All practical monitoring and follow-up steps will be taken to ensure complete and accurate data collection. Missing observations will be described in detail and evaluated for assessment of possible bias.

It is assumed that data will be missing at random. However, to examine this assumption, an analysis will be performed to compare baseline characteristics and symptomatic status (at earlier time points) between those participants with missing data and those who completed the study. Any missing observations will be described in detail and evaluated for assessment of possible bias.

For the primary effectiveness analysis, missing data will be imputed using the method of multiple imputation, with regression models that include relevant baseline covariates and the 3 month IPSS score (if available). Missing safety outcome data will be imputed using a similar multiple imputation method. A detailed description of the multiple imputation models including the full set of covariates to be used in the imputation model will be outlined in the SAP.

For the primary safety endpoint, a missing data sensitivity analysis will also be performed by comparing analyses using the following approach:

- 1). Available data only
- 2). “missing-equals-failure”
- 3). “missing-equal-success”
- 4). Last observation carried forward (LOCF)

For the primary effectiveness endpoint, a sensitivity analysis will be performed using:

- 1). LOCF
- 2). Same as baseline

In addition, a tipping point analysis will be performed for the primary study endpoints which will allow assessment of sensitivity without need for postulating any missing data mechanism. For the safety tipping point analysis, all possible combinations of missing data from the two arms will be considered, and the point at which significance is no longer achieved will be identified.

The planned sensitivity analyses for the primary outcome in the primary analysis population will be described in further detail in the SAP.

All data collected on safety or adverse events will be reported to the extent it is available, regardless of the active/withdrawn status of participants.

4.8 Pooling of Site Data

The homogeneity of safety and effectiveness results across study sites will be examined and if no statistically significant heterogeneity is found, the results will be pooled. The primary justification for pooling is that study sites will be following the same Protocol, using the same device system, and following the same Instructions for Use/User Manual. Additionally, frequent contact and monitoring of the sites will be performed to ensure that all Study sites are evaluating participants and recording study results in a reliable and reproducible manner. It is not anticipated that any individual study site will dominate the study results. Therefore, it is believed that these procedures will help to ensure that the data from these study sites can be combined and analyzed as if generated at a single site.

To evaluate differences among sites in the study, a summary of important baseline variables, such as demographics, medical history and baseline clinical variables, will be presented by site to allow for easy comparison. Additionally, the summary will provide non-baseline variables by site and by treatment group for comparison of procedure variables and variables related to the primary and secondary endpoints.

For the primary effectiveness endpoint, analysis of variance or other methods will be used to determine heterogeneity of effect sizes across site. For the primary safety endpoint, heterogeneity will be assessed using logistic regression and a site \times treatment interaction term or similar test. If evidence of non-poolability is found, baseline and procedural variables found to be different between sites will serve as predictors in a logistic or linear regression that also includes as predictors the treatment assignment, site, and site-by-treatment interaction.

It is also noted that the evaluation of site effect will consider OUS (outside US) versus U.S.-based sites. Thus, another analysis of the site effect will consider the comparison between the results for these two geographical regions in order to determine whether this had an effect on the study findings.

Further explanation on poolability analyses will be described in the SAP.

5 RISK/BENEFIT ANALYSIS

The study protocol has been designed to provide the greatest benefits while assuring the safety of participating subjects by mitigating the occurrence, limiting the severity and ameliorating the effects of any possible adverse events. The following describes the benefits subjects will receive as well as possible adverse events which have been identified as risks and for which subjects will be carefully monitored.

5.1 Benefits

The primary potential benefit of participation is the potential occurrence of successful treatment of BPH using the study device. Additional benefits may be decreased pain, decreased need for urinary catheter postoperatively, and faster overall recovery.

